#### **6 STUDY INTERVENTION**

Study intervention is defined as any investigational intervention(s), marketed product(s), placebo, or medical device(s) intended to be administered to a study participant according to the study protocol.

Clinical supplies (study interventions provided by the Sponsor) will be packaged to support enrollment and replacement participants as required. When a replacement participant is required, the Sponsor or designee needs to be contacted prior to dosing the replacement supplies. Clinical supplies will be affixed with a clinical label in accordance with regulatory requirements.

# 6.1 Study Intervention(s) Administered

The study intervention(s) to be used in this study are outlined in Table 3.

Table 3 Study Interventions

Arm Name	Arm Type	Intervention Name	Туре	Dose Formulati on	Unit Dose Strength(s)	Dosage Level(s)	Route of Admin- istration	Regimen/ Treatment Period/ Vaccination Regimen	Use	IMP or NIMP/ AxMP	Sourcing
Arm A – mRNA-5671/ V941 mono- therapy	Experimental	mRNA-5671/V941	Biological/V accine	Ampule	1.0 mg/mL	DL 1: 1.00 mg DL -1: 0.40 mg DL -2: 0.20 mg DL -3: 0.10 mg	IM	Q3W for up to 9 cycles	Test Product	IMP	Provided centrally by the Sponsor
Arm B and Cross-over mRNA-5671/ V941 + pembrolizumab	Experimental	mRNA-5671/V941	Biological/V accine	Ampule	1.0 mg/mL	DL 1: 1.00 mg DL -1: 0.40 mg DL -2: 0.20 mg DL -3: 0.10 mg	IM	Q3W for up to 9 cycles	Test Product	IMP	Provided centrally by the Sponsor
Arm B and Cross-over mRNA-5671/ V941 + pembrolizumab	Active Comparator	Pembrolizumab	Biological/V accine	Ampule	25 mg/mL	200 mg	IV Infusion	Q3W for up to 35 cycles	Compar ator	IMP	Provided centrally by the Sponsor

AxMP=auxiliary medicinal product; DL=dose level; IMP=investigational medicinal product; NIMP=non-investigational medicinal product; Q3W=every 3 weeks.

Participants may receive up to 9 total doses of mRNA-5671/V941 in either the monotherapy or combination arm.

Dose Levels DL -1, DL -2, and DL -3 will only be enrolled in the event that DLTs are observed in the starting dose (1.0 mg), per the mTPI design.

The classification of IMP and NIMP/AxMP in this table is based on guidance issued by the European Commission and applies to countries in the European Economic Area (EEA). Country differences with respect to the definition/classification of IMP and NIMP/AxMP may exist. In these circumstances, local legislation is followed.

PROTOCOL/AMENDMENT NO.: 001-08

All study interventions will be administered on an outpatient basis.

All products indicated in Table 3 will be provided centrally by the Sponsor or locally by the study site, subsidiary or designee, depending on local country operational or regulatory requirements.

For any commercially available product that is provided by the study site, subsidiary, or designee, every attempt will be made to source these supplies from a single lot/batch number. The study site is responsible for recording the lot number, manufacturer, and expiry date for any locally purchased product as per local guidelines unless otherwise instructed by the Sponsor.

Refer to Section 8.1.8 for details regarding administration of the study intervention.

#### 6.1.1 mRNA-5671/V941 Administration

For all participants, mRNA-5671/V941 will be administered by IM injection into the deltoid or thigh muscle (deltoid preferred). The Pharmacy Manual contains specific instructions for the preparation and administration of mRNA-5671/V941.

#### 6.1.2 Pembrolizumab Administration

For participants receiving mRNA-5671/V941 in combination with pembrolizumab, pembrolizumab will be administered at the study site as a 30-minute IV infusion of a 200 mg fixed dose on Day 1 of each 3-week (21-day) cycle 30 to 60 minutes following the administration of mRNA-5671/V941. Sites should make every effort to keep infusion duration as close to 30 minutes as possible. However, given the variability of infusion pumps from site to site, a window of 25 to 40 minutes is permitted for infusion duration. The Pharmacy Manual contains specific instructions for the preparation of the pembrolizumab infusion and administration of the infusion solution.

#### 6.2 Preparation/Handling/Storage/Accountability

# **6.2.1** Dose Preparation

Details on preparation and administration of mRNA-5671/V941 and pembrolizumab are provided in the Pharmacy Manual.

There are no specific calculations or evaluations required to be performed in order to administer the proper dose to each participant. The rationale for selection of doses to be used in this study is provided in Section 4.3.

# 6.2.2 Handling, Storage, and Accountability

The investigator or designee must confirm appropriate temperature conditions have been maintained during transit for all study intervention received, and any discrepancies are reported and resolved before use of the study intervention.

68

Only participants enrolled in the study may receive study intervention, and only authorized site staff may supply or administer study intervention. All study interventions must be stored in a secure, environmentally controlled, and monitored (manual or automated) area in accordance with the labeled storage conditions with access limited to the investigator and authorized site staff.

The investigator, institution, or the head of the medical institution (where applicable) is responsible for study intervention accountability, reconciliation, and record maintenance (ie, receipt, reconciliation, and final disposition records).

For all study sites, the local country Sponsor personnel or designee will provide appropriate documentation that must be completed for drug accountability and return, or local discard and destruction if appropriate. Where local discard and destruction is appropriate, the investigator is responsible for ensuring that a local discard/destruction procedure is documented.

The study site is responsible for recording the lot number, manufacturer, and expiry date for any locally purchased product (if applicable) as per local guidelines unless otherwise instructed by the Sponsor.

The investigator shall take responsibility for and shall take all steps to maintain appropriate records and ensure appropriate supply, storage, handling, distribution, and usage of study interventions in accordance with the protocol and any applicable laws and regulations.

# 6.3 Measures to Minimize Bias: Randomization and Blinding

# **6.3.1** Intervention Assignment

Treatment allocation will occur centrally using an interactive voice response system/integrated web response system (IVRS/IWRS). There are 2 treatment arms. Participants will be allocated to 1 of 2 treatment arms: mRNA-5671/V941 monotherapy (Arm A) or mRNA-5671/V941 in combination with pembrolizumab (Arm B) using an IVRS/IWRS in Part 1.

In Part 1 of the study, treatment will be allocated by nonrandom assignment. Enrollment into DL1 in Arm B will begin once all participants in DL1 Arm A complete the DLT evaluation (1 cycle) and DL1 of Arm A has been demonstrated to be safe and tolerable in this cohort. If/when both treatment arms are open for enrollment, IVRS/IWRS will alternate participant assignment between Arm A and Arm B starting with Arm A. An observation period of at least 7 days will occur between treatment initiation for the first participant and second participant within each dose level. A new dose cohort at DL -1, -2, or -3 may open for enrollment without delay once the 21-day DLT observation period of the previous dose cohort is completed and a dose de-escalation decision is made.

Participants on Arm A, who have radiological evidence of disease progression may be allowed to crossover to Arm B, at the investigator's discretion and after consultation with and approval by the Sponsor. Cohort assignment of crossover participants will be determined

at time of crossover by the Sponsor based on safety evaluation of the combination therapy cohorts. Refer to Section 4.1 for more information regarding eligibility for crossover.

When Part 2 is open for enrollment, IVRS/IWRS will assign participants to 1 of 3 cohorts by tumor type.

In a situation where reallocation/rerandomization of participants is planned (eg, study extension periods), the reallocation/rerandomization will be based on a new allocation/randomization schedule; however, each participant will retain his/her original treatment/randomization number. Only the study intervention regimen associated with the reallocation/rerandomization period or phase may change.

#### 6.3.2 Stratification

In Part 1 of the study, no stratification based on age, sex, or other characteristics will be used.

In Part 2 of the study, treatment allocation will be stratified according to the following factors:

1. Tumor type: Non-Small Cell Lung Cancer, Colorectal Cancer or Pancreatic Adenocarcinoma

## 6.3.3 Blinding

This is an open-label study; therefore, the Sponsor, investigator, and participant will know the intervention administered.

#### **6.4** Study Intervention Compliance

Administration of study medication(s) will be witnessed by the investigator and/or study staff. The total volume of study medication infused will be compared with the total volume prepared to determine compliance with each dose administered.

Interruptions from the protocol-specified treatment plan for more than 12 weeks for nondrugrelated or administrative reasons require consultation between the investigator and the Sponsor and written documentation of the collaborative decision on participant management.

# 6.5 Concomitant Therapy

Medications or vaccinations specifically prohibited in the exclusion criteria are not allowed during the ongoing study. If there is a clinical indication for any medication or vaccination specifically prohibited, discontinuation from study therapy or vaccination may be required. The investigator should discuss any questions regarding this with the Sponsor's Clinical Director. The final decision on any supportive therapy or vaccination rests with the investigator and/or the participant's primary physician. However, the decision to continue the participant on study intervention requires the mutual agreement of the investigator, the Sponsor, and the participant.

## **6.5.1** Acceptable Concomitant Medications

Treatment by local surgery and/or radiation therapy of isolated or symptomatic progressing lesions in the setting of improving baseline disease may be permitted for palliative or potentially curative management following completion of Cycle 2. Subsequently, all interventions, including continuation of study intervention, should be discussed with the Sponsor Clinical Director or designee.

#### 6.5.2 Prohibited Concomitant Medications

Participants are prohibited from receiving the following therapies during the Screening and Treatment Phases of this trial:

- Antineoplastic systemic chemotherapy or biological therapy not specified in this protocol
- Immunotherapy not specified in this protocol
- Chemotherapy not specified in this protocol
- Investigational agents other than pembrolizumab or mRNA-5671/V941
- Radiation therapy

Note: Radiation therapy to a symptomatic solitary lesion or to the brain may be allowed at the investigator's discretion after the DLT observation period in order for the participant to be considered evaluable for DLT.

• Live vaccines within 30 days prior to the first dose of study intervention and while participating in the study. Examples of live vaccines include, but are not limited to, the following: measles, mumps, rubella, varicella/zoster, yellow fever, rabies, BCG, and typhoid vaccine. Seasonal influenza vaccines for injection are generally killed virus vaccines and are allowed; however, intranasal influenza vaccines (eg, FluMist®) are live attenuated vaccines and are not allowed.

Note: Any licensed COVID-19 vaccine (including for Emergency Use) in a particular country is allowed in the study as long as they are mRNA vaccines, adenoviral vaccines, or inactivated vaccines. These vaccines will be treated just as any other concomitant therapy.

Investigational vaccines (ie, those not licensed or approved for Emergency Use) are not allowed.

 Systemic glucocorticoids for any purpose other than to modulate symptoms from an ECI that is suspected to have an immunologic etiology. The use of physiologic doses of corticosteroids may be approved after consultation with and approval by the Sponsor. • Granulocyte-colony stimulating factors and erythropoietin should not be used prophylactically during the DLT evaluation period. Use of prophylactic colony stimulating factors may be considered thereafter following consultation with and approval by the Sponsor.

Participants who, in the assessment of the Investigator, require the use of any of the aforementioned treatments for clinical management should be removed from the study.

All treatments that the investigator considers necessary for a participant's welfare may be administered at the discretion of the investigator in keeping with the community standards of medical care. All concomitant medication will be recorded on the eCRF including all prescription, over-the-counter (OTC) products, herbal supplements, and IV medications and fluids. If changes occur during the study period, documentation of drug dosage, frequency, route, and date should also be included on the eCRF.

All concomitant medications received within 28 days prior to the first dose of study intervention and up to 30 days after the last dose of study intervention should be recorded. Concomitant medications administered 30 days after the last dose of study intervention should be recorded for SAEs and events of clinical interest (ECIs) as defined in Section 8.4.

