## 6.5.3.2 Pembrolizumab Supportive Care Guidelines

Participants should receive appropriate supportive care measures as deemed necessary by the treating investigator. Suggested supportive care measures for the management of AEs with potential immunologic etiology are outlined along with the dose modification guidelines in Section 6.6, Table 5. Where appropriate, these guidelines include the use of oral or IV treatment with corticosteroids, as well as additional anti-inflammatory agents if symptoms do not improve with administration of corticosteroids. Note that several courses of steroid tapering may be necessary as symptoms may worsen when the steroid dose is decreased. For each disorder, attempts should be made to rule out other causes such as metastatic disease or bacterial or viral infection, which might require additional supportive care. The treatment guidelines are intended to be applied when the investigator determines the events to be related to pembrolizumab.

Note: If after the evaluation of the event, it is determined not to be related to pembrolizumab, the investigator does not need to follow the treatment guidance. Refer to Table 5 in Section 6.6 for guidelines regarding dose modification and supportive care.

It may be necessary to perform conditional procedures such as bronchoscopy, endoscopy, or skin photography as part of evaluation of the event.

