# 8.4.7 Events of Clinical Interest (ECIs)

Selected nonserious and SAEs are also known as ECIs and must be reported to the Sponsor.

Events of clinical interest for this study include:

- 1. An overdose of Sponsor's product, as defined in Section 8.5, that is not associated with clinical symptoms or abnormal laboratory results.
- 2. An elevated AST or ALT lab value that is greater than or equal to 3X the upper limit of normal and an elevated total bilirubin lab value that is greater than or equal to 2X the upper limit of normal and, at the same time, an alkaline phosphatase lab value that is less than 2X the upper limit of normal, as determined by way of protocol-specified laboratory testing or unscheduled laboratory testing.\*

\*Note: These criteria are based upon available regulatory guidance documents. The purpose of the criteria is to specify a threshold of abnormal hepatic tests that must trigger an additional evaluation for an underlying etiology. The study site guidance for assessment and follow up of these criteria can be found in the Investigator Study File Binder (or equivalent).

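### Section 6.5.2 limits its steroid exception to ECIs, so read literally it removes participants whom Tables 4 and 5 allow to be treated and restarted

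*Combined protocol and SAP*

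**What the plan says.** Section 6.5.2 lists therapies barred during Screening and Treatment. Among them are "Systemic glucocorticoids for any purpose other than to modulate symptoms from an ECI that is suspected to have an immunologic etiology". One further exception follows: "The use of physiologic doses of corticosteroids may be approved after consultation with and approval by the Sponsor". The list closes by saying that participants who, in the investigator's assessment, "require the use of any of the aforementioned treatments for clinical management should be removed from the study".

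ECI is a defined term. The same section says that medication given from 30 days after the last dose "should be recorded for SAEs and events of clinical interest (ECIs) as defined in Section 8.4". Section 8.4.7 then names two events. The first is "An overdose of Sponsor's product, as defined in Section 8.5, that is not associated with clinical symptoms or abnormal laboratory results". The second begins "An elevated AST or ALT lab value that is greater than or equal to 3X the upper limit of normal and an elevated total bilirubin" and also requires bilirubin of at least 2 times the upper limit of normal with alkaline phosphatase below 2 times that limit.

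Other sections direct or allow steroids without any ECI condition. Section 6.5.3.2 says that suggested measures for "management of AEs with potential immunologic etiology are outlined along with the dose modification guidelines in Section 6.6, Table 5". Table 5 gives steroid doses by event and grade, tells sites to withhold treatment, and lets it resume once the event is Grade 1 or lower after the taper. Section 6.6.3 applies Table 5 to immune-related AEs (irAEs) of the vaccine as well. Table 4 lists corticosteroids among the options for Grade 3 CRS and allows restart after discussion with the Sponsor.

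**The concern.** A participant with a first Grade 2 colitis who is treated exactly as Table 5 directs has received a systemic steroid that 6.5.2 prohibits. One part of the protocol says to hold, treat and consider resuming. Another says that the participant should be removed. The word used for removal also matches neither of the two defined statuses, which are stopping study intervention (Section 7.1) and withdrawal from the study (Section 7.2).

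What is at stake is consistent handling. A hold at one site could be a permanent stop at another, and stopping treatment because of an AE is one of the primary endpoints in Section 3. A participant who could have resumed might also lose further treatment without a medical reason.

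**Working it through.** The plan has no figure to reproduce here. The check compares the provisions and adds one dose calculation.

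**Step 1. What the ECI exception covers.** Of the two ECIs in 8.4.7, the overdose item is by definition free of symptoms and abnormal laboratory results, so there is nothing immunologic to treat. Only the liver-test item could be immunologic.

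**Step 2. Whether the physiologic-dose exception helps.** Table 5 directs 1-2 mg/kg prednisone for the three main events. The toxicology section (2.2.1.2) uses an average human weight of 70 kg:

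- 1 mg/kg × 70 kg = 70 mg/day, and 2 mg/kg × 70 kg = 140 mg/day.
- Exclusion criterion 12 sets a limit of 10 mg/day for chronic steroids. 70/10 = 7 and 140/10 = 14, so the dose is 7 to 14 times that limit.
- If weight is assumed to run from 50 to 100 kg, the range is 1 × 50 = 50 to 2 × 100 = 200 mg/day.
- The Grade 2 hepatic dose of 0.5-1 mg/kg gives 35-70 mg/day, or 3.5 to 7 times the limit.

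The 10 mg limit does not define a physiologic dose, and the 70 kg comes from a rat-to-human conversion, so the ratio is only a guide. Exclusion criterion 4 uses the term physiologic for replacement in adrenal or pituitary insufficiency, and treatment of colitis or pneumonitis is not replacement.

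**Step 3. Side by side.**

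| Event | Tables 4 to 6 | Covered by a 6.5.2 exception? | Conflict |
|---|---|---|---|
| Pneumonitis, Grade 2 | Hold, 1-2 mg/kg, may resume | No | Clear |
| Diarrhea/colitis, Grade 2-3 | Hold, 1-2 mg/kg, may resume | No | Clear |
| Nephritis, Grade 2 | Hold, 1-2 mg/kg, may resume | No | Clear |
| Myocarditis, Grade 1 | Hold, steroids by severity | No | If steroids are given |
| Other irAEs, persistent Grade 2 | Hold, steroids by severity | No | If steroids are given |
| Other irAEs, Grade 3 | Hold or discontinue, steroids by severity | No | If steroids are given and treatment is only held |
| Hepatic, Grade 2 | Hold, 0.5-1 mg/kg, may resume | Only if the combined ECI criterion is met | Partial |
| CRS, Grade 3 (Table 4) | Steroids optional, restart possible | No | If steroids are given |
| Hypophysitis | Steroids and hormone replacement | Possibly, as physiologic dosing | Not counted |
| Infusion reaction, Grade 3-4 (Table 6) | Steroids optional, permanent stop | No | None on resumption |

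The hepatic row is partial because Table 5 acts on transaminases or bilirubin, whereas the ECI needs both. The entry for other irAEs at Grade 3 assumes that the steroid cell in the printed table spans that row.

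**Result.** Table 5 has three clear conflicts, three conditional ones and one partial one. Table 4 adds one conditional case.

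**The case against.** The strongest reply is that the ECI list is open. Section 8.4.7 says that the events *include* the two items, Table 8 has a row for ECIs that are not liver-injury events, and an exception for immunologic ECIs has little content if the list is closed. This weakens the literal reading but does not remove it. The overdose item already accounts for the Table 8 row, and even an open list names no irAE and no CRS.

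The second reply is that nearby text shows the intent. The removal sentence is advisory and depends on the investigator's judgment. Section 6.5.2 goes on to say: "All treatments that the investigator considers necessary for a participant's welfare may be administered at the discretion of the investigator". Section 6.5 says only that stopping study therapy may be required, and it leaves continuation to agreement between investigator, Sponsor and participant. Section 6.5.3.2 and Table 5 are the more specific rules. This largely stands: the intended exception is almost certainly irAEs, and sites would probably follow the tables. But permission to give a drug does not cancel a sentence about participants who need it, and the softer wording of 6.5 is a further mismatch with 6.5.2.

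A reader might also infer that removal means Section 7.2 withdrawal, so that follow-up is lost. The documents give this little support. The only mandatory ground in 7.2 is withdrawn consent, and 7.1 keeps those who stop intervention early in the study. Section 4.1 speaks of discontinuation from the study at the end of treatment and then describes safety, imaging and survival follow-up. Section 8.1.5.2 moves participants who start other anticancer therapy into survival follow-up.

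**Conclusion.** The wording of 6.5.2 is wrong as written, and the consequence is minor. If followed literally, it turns a hold into a removal in three Table 5 rows, and under stated conditions in four more rows and in Grade 3 CRS. This assumes that ECI has the content given in 8.4.7. The documents give no rate of steroid use and show no site that applied 6.5.2 literally, so no participant count and no direction of bias can be stated. For the primary endpoint, what remains is possible inconsistency between holding and stopping.

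Three stronger inferences are not supported:

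- **A hold of four cycles under Table 5** (12 weeks / 3 weeks). The 12 weeks run from the last treatment. With dosing every 3 weeks, resumption at week 12 misses the doses at weeks 3, 6 and 9, which is three doses.
- **A separate recorded reason of prohibited medication.** Section 7.1 lists no such reason, and in these cases the steroid is given for an AE.
- **Harm to dose finding.** Under Section 6.6.2, related nonhematologic events of Grade 3 or higher are generally DLTs already (item 5), and so is a delay of more than 2 weeks in starting Cycle 2 because of related toxicity (item 8). Cycle 2 is due on Day 22, so item 8 applies after Day 22 + 14 = Day 36. A taper of at least 28 days that starts after Day 8 runs past Day 36 (8 + 28 = 36). Most lower-grade Cycle 1 cases would therefore count in any event if treatment waits for the taper.

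**What to change.** Make three changes in 6.5.2:

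1. Replace the ECI condition in the steroid exception with *an AE suspected to have an immunologic etiology, or CRS, managed per Tables 4 and 5*.
2. Replace removal from the study with *discontinued from study intervention, with follow-up continuing per Section 7.1*.
3. State that steroids given under Tables 4 and 5 do not trigger that sentence.

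Do not add a general clause allowing continuation by agreement. The sentence also covers non-study anticancer therapy, for which Section 8.1.5.2 says that study treatment should be discontinued. Infusion reactions need no mention, because Table 6 lists steroids only at grades that already end treatment.

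Optionally, list in the clinical study report the participants who stopped treatment after steroids for an event at a grade where Table 5 calls for a hold, with the recorded reason.

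The cost is two reworded sentences, one clarifying statement and, if wanted, one listing from data already collected. No procedures or participants are added. Amendment 8 prepares the close-out of the study, so the prospective benefit is small and the listing has the most practical value.
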